## INSTRUCTIONS:

- Use this “*TEMPLATE PROTOCOL (HRP-503)*” to prepare a study protocol outlining your research plan.
- Depending on the nature of your study, some major sections might not be applicable to your research. If so, simply mark as “N/A.” For example, a simple survey might have many sections with “N/A.” For subsections (e.g., 1.x or 8.x) you can mark as “N/A” if you are certain that the subsection is not applicable.
- Once the IRB/HRPP approves your submission, your latest approved version of the protocol will be stored in the IRB Protocol Management online system.
- If your research plan changes and you need to modify the protocol, please submit an amendment to Protocol Management with the requested modifications. Download your current protocol from Protocol Management and indicate the changes/revisions using the track changes feature in order to make review of the modifications easier to follow. If you are unable to use track changes, please create a new paragraph wherever you need to make a change, and indicate “Amendment: Date” before making a change to any section. Protocol management will store the older versions of your protocol if the IRB or HRPP staff need to compare them during the review.

## REVISION HISTORY:

*Use this table to keep track of changes. Add more rows as needed.*

Revision #	Version Date	Brief Summary of Changes (i.e., the different sections)	Consent Change?
1	28 June, 2021	Requested additional or clarifying details added to sections 8 (most), 9.4, 10.0, 12.2 and 12.3, 15.4, 21.0, 24.1 and 25.2	Yes
2	25 July, 2021	Requested additional details added to sections 7.3, 8.3, 9 and 15.4. Typos corrected. DOB and a few edits made to consent, advertisement flyer and several study forms.	Yes
3	28 Sept, 2021	Completed changes suggested by Board specifically related to the addition of coronary artery disease as an exclusion factor (section 12) and clarification on the health history questionnaire (section 8.1 and 20), GPS (section 8.1) and pregnancy test with the DXA (Table in section 8 and in consent. Clarified payment info (discussed on IRB Call in section 15.4; Made requested changes to consent (which included carefully reading over for clarity and typos and editing factors related to the above); Made required changes to recruitment flyer; Added the doctoral student (previously listed as TBA) who will be in charge of the protocol ([name]).	Yes
4	Nov 1, 2021	We have made minor editorial and logistic questions to the protocol and consent that includes: a) minor changes in screening (we will use HIPA compliant zoom vs telephone when possible) and the screening form (updated form uploaded); b) minor changes to the snack items offered (complete list uploaded), walking economy speed, VO2max protocol, and resistance training exercises; and c) inserted language that participants would not	Yes

		be informed of the macronutrient composition of the two snack groups. We also include new/updated participant instructions for use of the smartwatch, CGM and 24 h urine collection.	
5	25 January	We added information about the Eating Attitudes Questionnaire that will be used to help screen for eating disorders and disordered eating to sections 12.2 and 19.5. We uploaded the referral sheet that will be provided to anyone who scores higher than a 20 on this test.	Yes
6	7 April	We added abnormal serum lipids as an exclusion criterion (section 12.0, page 26). We added an additional questionnaire at baseline to evaluate vitamin D status as a baseline health outcome and a study exit survey at study conclusion (Table 1 and section 8.2). We clarified that we will also measure iodine concentration in the urine samples to help interpret thyroid and other hormone concentrations at baseline and study end. We would also like to increase our potential sample size to 40 from 32 to account for a possibility of drop outs and ensure we have a complete sample of 32 participants; we still plan on recruiting as close to half men and half women as possible with a balance between our two intervention groups. We also added an exit survey. We uploaded the Vitamin D Food Frequency and Lifestyle Questionnaire and the Exit Survey.	Yes

## 1.0 Study Summary

Study Title	Exploring the Role of Peanuts in Enhancing Healthy Weight Gain in Athletic Individuals
Study Design	Randomly Assigned Intervention Study
Primary Objective	Determine the efficacy of the standard hypercaloric sports performance diet (500 kcal surplus energy, adequate protein and carbohydrate, judicious fat) and weight training regimen with excess calories from peanut foods or high-carbohydrate snack foods on weight and lean mass gains over 10 weeks in athletic men and women desiring weight gain.
Secondary Objective(s)	Secondary Aim: Evaluate the ease and acceptability of whole peanuts, peanut butter and peanut-based healthy snacks relative to high-carbohydrate snacks as part of the standard hypercaloric regimen. Exploratory Aim: Examine the effect of potential adaptive factors (increased resting metabolism, decreased appetite) and individual characteristics (sex, age, training history, somatotype) on weight and lean mass gains.
Study Population	Athletic and military men and women who desire weight gain primarily as lean mass to improve performance and/or effectiveness in sport/military endeavors.
Sample Size	32 (16 men and 16 women)
Research Intervention(s)/ Investigational Agent(s)	Men and women will be randomly assigned to a peanut intervention or control group (8 men and 8 women per group); Each group will undergo a 10-wk diet and weight training regimen designed to promote healthy weight gain.
Study Duration for Individual Participants	12 to 13 weeks including screening, baseline testing, the 10-week intervention and post-testing
Acronyms and Definitions	DXA, Dual-Energy X-ray Absorptiometry; TSH, thyroid-stimulating hormone; CBC, complete blood count; RMR, resting metabolic rate; REE, resting energy expenditure; VO 2 max, maximal oxygen uptake during exercise, also known as aerobic capacity; Reps; repetitions; CGM, continuous glucose monitoring; ISAK, International Standards for Anthropometric Assessment; ACSM, American College of Sports Medicine; IUSCA, International Universities Strength and Conditioning Association; HIP Laboratory, Human Integrated Physiology Laboratory; NEM Laboratory, Nutrition and Exercise Metabolism Laboratory

## 2.0 Objectives

### 2.1 *Describe the purpose, specific aims, or objectives of this study:*

- 1) Determine the efficacy of the standard hypercaloric sports performance diet (500 kcal surplus energy, adequate protein and carbohydrate, judicious fat) and resistance training regimen with excess calories from peanut foods or high-carbohydrate snack foods on weight and lean mass gains over a 10-wk period in athletic men and women desiring weight gain.
- 2) Evaluate the ease and acceptability of whole peanuts, peanut butter and peanut-based healthy snacks relative to high-carbohydrate snacks as part of the standard hypercaloric regimen.
- 3) Explore the effect of potential adaptive factors (increased resting metabolism, decreased appetite) and individual characteristics (sex, age, training history, somatotype) on weight and lean mass gains.

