### 2.2 *State the hypotheses to be tested:*

The standard hypercaloric sports performance diet (500 kcal surplus energy, adequate protein and carbohydrate, judicious fat) and resistance training regimen with excess calories from peanut foods or high-carbohydrate snack foods will result in an average weight gain of 1/2 pound/week in both men and women, with the majority of that gain as lean (fat-free mass) mass.

Weight gain will be more efficient when the excess calories are from peanut foods (compared to control, high-carbohydrate foods) which will be better accepted than the control snacks.

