Although methods of weight gain in athletes were heavily discussed in the mid to late 90's (Butterfield, Kleiner et al. 1995, Grandjean 1999), few studies have been conducted over the past 20 years, other than those specifically focusing on protein intake and timing on acute muscle protein synthesis (Phillips and Van Loon 2011). In one of the few studies conducted, Bartels and colleagues (Bartels, Lamb et al. 1989) found that the addition of 500 extra kcal/day during 9 weeks of heavy resistance training resulted in approximately 1/2 lb increase in lean mass/wk with no corresponding increase in body fat percentage in 12 male weight trainers. Body weight increases did not differ whether the hypercaloric diet was 45 versus 65% carbohydrate. Another semi-controlled study of Kreider et al. (Kreider, Klesges et al. 1996) examined whether supplementing the diet with one of two commercially-available weight gain powders for 28 days compared to a maltodextrin placebo influenced lean tissue accretion. Carbohydrate ingestion alone promoted a non-significant increase in lean weight of 1.47 lb (670 g) with increase in body fat weight; while ingestion of one commercial powder produced identical increases (665 g) but also an increase in body fat. The other powder promoted a significant increase of 1.56 lb (707 g) predominately as lean tissue. A more recent study by Garthe et al (Garthe, Raastad et al. 2011) examined the effect of nutritional counselling (designed to create a 500 kcal/day surplus) compared to ad libitum dietary intake on changes in body composition during an 8-12 week focused resistance training period in 21 elite Norwegian athletes (including 4 women). Individually-prescribed hypercaloric meal plans and counseling resulted in successful short and long-term gains in total body and lean mass. To our knowledge, no studies have evaluated intentional weight gain in active women (who may also desire weight gain (Minnick, Raffoul et al. 2020)) or focused on the health implications of such gain in athletes.

Benefit of Peanuts and Peanut Products in Healthy Weight Gain. Research and observations by sports dietitians suggest that active individuals interested in weight gain

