With increased prevalence of overweight and obesity in the U.S and worldwide, emphasis on understanding healthy weight gain in both the general population and among athletes and military personnel has been largely ignored. However, a recent survey of close to 977,000 Canadian adults, aged 17-32 years, found that ~23% of men and 6% of women reported attempting to gain weight in the past 12 months (Minnick, Raffoul et al. 2020). In athletes (Garthe and Maughan 2018) and military personnel (Bukhari, DiChiara et al. 2021), desire to gain weight is a top reason reported for supplement use. Attempts to gain weight included eating more overall and eating more protein (Minnick, Raffoul et al. 2020) through consumption of foods that are often ultra-processed, and likely to

have negative health effects. Previous studies by [name] group found that weight gain of 5 kg using such foods increased systolic and diastolic blood pressure even in those who were relatively fit (Gentile, Orr et al. 2007). The proposed study would serve as an important first step in helping understand the gaps in knowledge related to healthy weight gain. Findings would be of interest to sports and military dietitians and would be expected to lead to better understanding of the energy surplus needed to overcome metabolic adaptation and develop more targeted weight prescriptions. Results would inform the design of more effective weight gain meal plans, not only in athletes and military personnel, but also in older individuals and in clinical populations where promotion of weight gain is advocated. Future trials based on findings of the proposed study will likely explore benefits of peanut products in healthy weight in a variety of populations

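### Objective 1 asks for the efficacy of a diet-plus-training package that both arms receive, so the overall gain is an uncontrolled before-after estimate and only the snack contrast is randomised

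*Combined protocol and SAP*

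**What the plan says.** Section 2.1 sets the first objective as to "Determine the efficacy of the standard hypercaloric sports performance diet", defined by a 500 kcal surplus, together with the resistance training regimen, with the extra calories coming from either peanut foods or high-carbohydrate snacks, on weight and lean mass gain over 10 weeks. Section 1.0 gives the same text as the primary objective.

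Section 2.2 has two hypotheses of different kinds. The first is an absolute statement with no comparator: the regimen "will result in an average weight gain of 1/2 pound/week in both men and women", most of it lean. The second is comparative: peanut snacks should give more efficient gain than the control snacks and be better accepted.

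On design, section 1.0 says "Each group will undergo a 10-wk diet and weight training regimen designed to promote healthy weight gain". Sections 5.1, 8.1 and 8.2 give both arms 500 kcal/day above weight maintenance and the same supervised training three days a week. The arms differ in the snack: about 15 g of protein in the peanut snacks and about 5 g in the control snacks, at the same energy.

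Section 5.2 assigns repeated measures ANOVA, by group and over time, to Aim 1. Section 3.3 expects the findings to lead to "better understanding of the energy surplus needed to overcome metabolic adaptation".

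**The concern.** A claim that a regimen is efficacious is a claim about what would have happened without it. Nothing in this trial shows that. Every participant has the regimen from the start, and the only measurement before it is a single baseline.

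The protocol itself names several other reasons why weight might rise:

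- Section 12.2 enrols people who already want to gain at least 5 lb.
- Section 8.1 tells those in sport or military training to keep up their normal training alongside the study programme.
- Section 13.1 admits university athletes only in their off-season.
- Section 16.1 allows withdrawal of people who do not eat the snacks or attend sessions, which could leave compliers in the before-after average.

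What is at stake is what the trial may conclude. Section 5.2 does not say which ANOVA term answers Aim 1. An analyst who follows it could find a significant time effect and take that as the answer to an objective worded as efficacy. Section 3.3 looks ahead to more targeted weight prescriptions, so the distinction matters for how the result is used.

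**Working it through.** **1. Layout.** Section 1.0 gives 2 arms × (8 men + 8 women) = 2 × 16 = 32. The sample size rests on feasibility (section 14.1). There is no power calculation to reproduce.

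**2. What the design can estimate.** Write one row per participant, with columns for intercept, surplus, training and peanut:

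- control arm (16 rows): 1, 1, 1, 0
- peanut arm (16 rows): 1, 1, 1, 1

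The matrix has 4 columns but rank 2. Surplus and training equal 1 for everyone, so they cannot be told apart from the intercept, which is the mean change over time. Two quantities are estimable: the overall before-after change and the peanut-minus-control difference. Treating diet and training as one package removes a column but does not help, because the package column is still 1 for everyone.

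**3. Is there an untreated period?** Table 1 in section 8 has one baseline, then weeks 3, 7 and 11. The diet history before enrolment (section 12.2) checks that energy and protein intake are adequate. It is not a measured period of stable weight. So there is no within-person control either.

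**4. Size of the uncontrolled quantity.** The first hypothesis implies 0.5 lb/week × 10 weeks = 5 lb. All of it is before-after change.

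**5. Precision of the two estimable quantities.** Let SD be the within-arm standard deviation of the change to week 11, assumed equal in the arms, with 16 completers per arm.

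- Overall change: standard error = SD/√32 = 0.177 SD.
- Peanut minus control: standard error = SD × √(2/16) = 0.354 SD, twice as large.
- Detectable difference at 80% power, two-sided 0.05 (the plan does not state sidedness): (1.960 + 0.842) × √(2/16) = 0.99 SD, or 1.02 SD by the t test.
- Power of the randomised contrast: 0.29 at 0.5 SD and 0.62 at 0.8 SD.
- With 20 completers per arm, if all 40 allowed by section 14 finish, the detectable difference is 0.89 SD.

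The uncontrolled quantity is thus the more precise one. The randomised contrast may well be inconclusive, which makes it more likely that the time effect becomes the headline.

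**6. Surplus level.** There is one target, 500 kcal/day. Section 8.2 adjusts it upward with weight gain and gives no separate rule for either arm. Differences in surplus between participants would therefore follow the outcome and not the randomisation.

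**The case against.** Four points on the other side deserve weight.

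*The objective concerns a package.* Objective 1 and the first hypothesis name diet and training together. A reader might go further and infer that the trial fails to apportion the 5 lb between surplus and training, and so that the share due to the surplus is wholly unknown. The protocol never sets out to make that split, so failing to make it is not the defect. The defect is narrower: the package as a whole has no concurrent control.

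*The gain can be estimated.* A reader might infer that the trial can only compare snacks. That is too strong. Serial weights and DXA scans can estimate the overall gain and set it against 1/2 lb/week, which is what the first hypothesis asks. What is missing is the licence to call that gain efficacy.

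*Background gain may be small.* Participants must have resistance-trained within the last year and be currently active (section 12.2). Section 3.1 cites yearly gains of only 1 to 3% after the first year of training. At an assumed 150 lb with linear accrual, that is 150 × 0.01 × 10/52 = 0.3 lb to 150 × 0.03 × 10/52 = 0.9 lb in 10 weeks (0.2 to 1.2 lb for assumed weights of 110 to 200 lb). The same passage gives up to 20% in the first year, or 150 × 0.20 × 10/52 = 5.8 lb (4.2 to 7.7 lb). The figures concern young male body builders and football players and do not separate diet from training. They make it less plausible that training explains the whole gain, and the documents do not show that it does. They cannot stand in for a control either.

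*The background and section 3.3 are more measured than they may look.* Section 3.1 cites one study that tested a planned surplus "compared to ad libitum dietary intake on changes in body composition", but also a 9-week trial in which the extra 500 kcal and heavy training were common and the diets differed in carbohydrate share. Ad libitum intake is therefore not presented as the one required comparator. Section 3.3 calls this study a first step and leaves more to later trials. It does not promise to determine the surplus needed, and intake and resting metabolism are measured, so exploratory information is possible.

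These points narrow the concern. None of them turns a before-after change into efficacy.

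**Conclusion.** The concern holds in this form. The design cannot deliver the efficacy of the combined surplus diet and training, because both arms receive it and no arm or period lacks it. The overall gain, 5 lb if the first hypothesis is right, is an uncontrolled before-after estimate. Only the peanut-versus-high-carbohydrate contrast is randomised evidence, and at 16 per arm it is sensitive to differences of about 1 SD. That contrast compares the snacks as supplied, including their difference in protein.

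The conclusion about identification rests on the documents alone and needs no assumed figure. The precision figures assume a two-sided 5% level, a common SD and 16 completers per arm. The documents do not say how the time effect will be reported, so its being presented as efficacy is a risk that the wording leaves open, not a stated intention.

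**What to change.** All changes are to wording.

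- **Sections 1.0 and 2.1:** restate objective 1 as comparing weight and fat-free mass gain between peanut and high-carbohydrate snacks as the source of the extra calories, during a common 10-week training programme.
- **Section 5.2:** name the group-by-time contrast as the only efficacy inference for Aim 1. It would be fair to state there what 16 per arm can detect.
- **Section 2.2, first hypothesis:** keep it as a descriptive benchmark. Report the overall before-after gain with a 95% confidence interval against 1/2 lb/week, as the change seen with the whole package and not as efficacy of the diet, the surplus or the training.
- **Section 3.3:** mark the expectation about the energy surplus needed as hypothesis-generating, since there is one surplus target, adjusted upward with weight gain in both arms alike.

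Cost: a protocol amendment and matching text in the report, with no extra participants, visits or measurements. The price is a narrower headline claim. Keeping the efficacy claim would need a concurrent arm without the package. At the same 16 per arm, that is 3 × 16 = 48 completers in place of 32.

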Questionnaire-Snack acceptability & exit survey				x

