**Dietary Intervention:** The peanut group will be provided with a variety of whole and laboratory-prepared peanut-containing snacks to meet their daily excess energy. The snacks will be calculated to contain 500+- 10 kcal and 15 grams of protein (using Nutrition Data System for Research nutrient analysis software). A complete list of these snacks is uploaded as supplemental files. The control group will be provided similar 500 kcal high carbohydrate containing snacks that contain ~5 g protein.. Participants will be informed that they are in the peanut or non-peanut group but the dietary composition differences between these snacks will not be mentioned or discussed. Participants will be encouraged to consume snacks within an hour of resistance training and/or before bed (Phillips and Van Loon 2011). Participants in both groups will be allowed to select from several different snack options offered each week. Participants will also undergo weekly assessments during one of the resistance training sessions to ensure compliance and adequate progress with excess energy adjusted upward with weight gain to avoid the potential effects of acute energy imbalance due to total body/lean mass gain and help ensure adequate (~0.5 pounds/week) but not excessive (>1.5 #/week) weight gain.

**Daily Snack and Exercise Tracking Logs:** Participants will keep daily record of consumption of the provided snacks as well as other exercise training undertaken using a simple snack and exercise tracking log. These logs require participants to place a check mark by snacks consumed and to quickly fill in time spent in other exercise training activities. Logs will be turned in to the researchers every two weeks during resistance training sessions.

**Strength and Fitness Testing:** Strength of a major upper and lower body group (i.e. bench press and leg press) will be assessed on the Nautilus equipment at the beginning and end (wk 11) of the 10-wk program by recording the maximal weight that can be lifted once correctly. The change in the aforementioned 80% RM value will also be documented for use as data points.

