#### Week 11 Final Testing Session (approximately 2 1/2 hours)

This session will be performed as outlined in the Baseline testing section. Blood will be drawn by venipuncture from a vein in the arm with the participant seated quietly in a phlebotomy chair. Blood will be analyzed for all hormones and metabolites analyzed at baseline except the CBC. Approximately 20 ml will be obtained for screening/baseline. Participants will also provide feedback related to the palatability and ease of consumption of the snacks they consumed on a questionnaire and also be asked to complete a brief exit survey.

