## **16.0 Withdrawal of Subjects**

*16.1 Describe circumstances under which you anticipate subjects could be withdrawn from the research without their consent:*

Participants could be withdrawn from the study if they are not showing up for appointments and/or training sessions, are not consuming the provided snacks, or are not completing or complying with all procedures. They also may be withdrawn if they develop an injury or illness that would prevent

them from doing everything that is expected for the study or which might compromise their health.

*16.2 If applicable, describe any procedures for orderly termination (e.g., discontinuation of a study drug or debriefing after a behavioral intervention):*

If a participant is not complying with the study, the PI or study coordinator will first discuss these difficulties with the participant and explain the importance of adhering to the intervention for the purpose of the study. If it is determined that the participant be terminated or discontinued from the study for reasons as described above, the PI will mitigate issues leading to these problems. The participant will be provided any information which is available to them (baseline body composition, fitness testing, resting metabolic rate). It will then be suggested that the study personnel part ways with the participant

*16.3 Describe procedures that you will follow when subjects withdraw from the research, including partial withdrawal from procedures with continued data collection (e.g., participant declines to continue with regular blood draws, but continues with periodic behavioral questionnaires):*

Any participant can discontinue participation at any point without consequence.

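### Aim 2 ratings cover only the snacks each participant chose to eat, so they are likely to flatter the named foods; the arm comparison is at risk only if the menus differ in breadth

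*Combined protocol and SAP*

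**What the plan says.** Section 2.1 sets a comparative aim that names particular foods: "Evaluate the ease and acceptability of whole peanuts, peanut butter and peanut-based healthy snacks relative to high-carbohydrate snacks". Section 2.2 adds a direction, that excess calories will come from peanut foods "which will be better accepted than the control snacks". Section 4.1 lists a snack rating among the primary endpoints, while section 1.0 calls the aim secondary.

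Three statements in section 8.2 determine what is measured:

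- Choice of snacks: "Participants in both groups will be allowed to select from several different snack options offered each week".
- What is rated at week 11: "feedback related to the palatability and ease of consumption of the snacks they consumed on a questionnaire". In Table 1 the row "Questionnaire-Snack acceptability & exit survey" is marked only in the week-11 column.
- Daily logs: "These logs require participants to place a check mark by snacks consumed". The text describes a record of what was eaten. It mentions no record of what was offered and declined.

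Menu sizes are not in the text: "A complete list of these snacks is uploaded as supplemental files". Section 5.2 assigns descriptive statistics to Aim 2, refers there only to the peanut foods, and does not mention choices or logs.

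**The concern.** The rating is conditional on choice, and choice depends on liking. A participant in the peanut arm who dislikes whole peanuts can take other items for ten weeks and never rate them. Two consequences follow, and they differ in strength.

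1. **Ratings of individual foods.** Each item is scored mainly by people willing to eat it. Its mean score is then likely to be higher than if everyone offered it had scored it. This applies in both arms and does not need unequal menus.
2. **The arm comparison.** A wider menu gives each person more chance of finding favourites. If one arm's menu were wider, its ratings could be higher with no true difference in liking. This is conditional on a difference that the text does not show.

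At stake is what Aim 2 can conclude. Without knowing how many people avoided an item, a high mean score cannot be told apart from a high score among a self-selected few.

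**Working it through.** The plan states no effect size, SD or power for Aim 2, so there is no figure to reproduce. The calculation below only shows how large the effect could be.

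**Inputs from the documents.** Self-selection in both arms and rating of consumed snacks (section 8.2); 16 participants per arm (section 8.1).

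**Assumptions.** Within a person, liking of the m menu items is independent normal with SD 1, with the same mean in both arms. Each person eats and rates the k items they expect to like best. Expected and actual liking correlate at rho. Menu sizes, k and rho are not in the documents.

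**Formula.** Mean rated liking minus mean liking of the whole menu = rho × (average of the k largest expected normal order statistics out of m). The items are exchangeable, so this is also the expected excess in one item's mean rating among those who rate it. On average a fraction k/m of the arm rates each item.

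**Step 1: level of the ratings, k = 2, rho = 1.**

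| Options m | Working | Excess (SD) | Average raters per item, 16 per arm |
|---|---|---|---|
| 4 | (1.029 + 0.297)/2 | 0.66 | 16 × 2/4 = 8 |
| 6 | (1.267 + 0.642)/2 | 0.95 | 16 × 2/6 ≈ 5 |
| 8 | (1.424 + 0.852)/2 | 1.14 | 16 × 2/8 = 4 |

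The excess is 0 if every item is rated (k = m) or if choice is unrelated to liking (rho = 0).

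**Step 2: difference between arms with equal true liking.**

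| Scenario | Working | Difference (SD) |
|---|---|---|
| Equal menus, same k and rho | identical terms | 0 |
| 8 v 4, three quarters eaten (6 and 3), rho = 1 | 0.38 − 0.34 | 0.04 |
| 8 v 4, half eaten (4 and 2), rho = 1 | 0.73 − 0.66 | 0.06 |
| 8 v 6, 3 or 4 items eaten, rho = 1 | 0.92 − 0.70; 0.73 − 0.48 | 0.21; 0.25 |
| 8 v 4, two items eaten, rho = 0.5 | 0.5 × 0.475 | 0.24 |
| 8 v 4, two items eaten, rho = 1 | 1.138 − 0.663 | 0.47 |

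The differences are taken from unrounded values. The 0.73 is (1.424 + 0.852 + 0.473 + 0.153)/4.

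The result depends heavily on whether people eat a fixed number of items or a fixed share of the menu. The documents do not say which is closer to the truth.

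**Outside the calculation.** Section 16.1 allows withdrawal of participants who "are not consuming the provided snacks, or are not completing or complying with all procedures". The questionnaire is scheduled only at week 11, so some people who liked the snacks least may give no rating at all. This acts in the same direction and is not sized here.

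**The case against.** A reader might infer that the peanut arm will look better accepted because its menu is wider, or that the acceptance hypothesis can be decided by menu breadth alone. The documents do not support that. Nothing says either menu is wider, both arms are described as choosing from several options, and the control snacks are called similar. With equal menus and equal selectivity the arm contrast is unbiased. The 0.47 SD figure needs an 8 v 4 split, exactly two items eaten over ten weeks, and perfect foreknowledge of liking. It is an upper illustration, not an estimate.

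Three further objections have force:

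- It is too strong to say that disliked items always go unrated. An item tried once and dropped was consumed and can be rated; only items never tried are lost.
- The questionnaire and exit survey were not seen. They may ask about avoided items, or about the regimen as a whole and not item by item. The protocol text, however, limits the feedback to what was consumed and does not say more.
- Aim 2 concerns acceptability within the weight-gain regimen, in which people choose their snacks. Rating what one chose is a reasonable answer to that pragmatic question. For the same reason choice frequency should not become the main measure: it shows preference within an arm, not which arm's snacks are better accepted.

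Section 5.2 assigns no significance test to Aim 2, so false-positive rates for such a test are not used here. What remains is that the aim names specific foods, the ratings come from self-selected eaters, and the plan provides no denominator by which a reader could see this.

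**Conclusion.** The point holds for the ratings of individual foods. As the protocol describes the measurement, items never chosen because of dislike go unrated, so scores for the foods named in Aim 2 are likely to lean favourable. The size depends on how selective people are. It is 0 if everyone eats everything, and about 0.66 to 1.14 SD of item liking if each person eats only two favourites out of 4 to 8.

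For the between-arm comparison the point is conditional. The distortion is 0 with equal menus. With 8 v 4 options it is about 0.06 SD when half of each menu is eaten and about 0.47 SD in the extreme case. All sizes rest on assumed menu sizes, independent item likings and an assumed link between choice and liking. If the uploaded lists show equal menus, and the uploaded form already covers items offered but not eaten, most of the concern falls away. The protocol should then say so.

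**What to change.** 1. On the week-11 form, list every item on the arm's menu, with a rating and an offered-but-not-eaten option.
2. Report each item's rating with the number who rated it out of the number offered it.
3. In section 5.2, for both arms, add times chosen divided by times offered, and portions eaten divided by portions supplied. Take these from the daily logs and a weekly record of the menu offered and portions supplied. Label them supporting, not main, measures of acceptability.
4. Offer the same number of options in each arm each week, and state this in section 8.2.

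The cost is a slightly longer form, a weekly menu record, and tabulation of logs that are already kept. No visit, sample size or randomisation step changes.
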